2.2. Study Endpoints

2.2.1. Efficacy Endpoints

The primary efficacy endpoint is:

- Mean change from start to end of KZR-616 treatment in the Total Improvement Score (TIS), which ranges from 0 to 100.

Secondary efficacy endpoints are:

- Proportion of patients with an increase ≥ 20 points on the TIS from start to end of KZR-616 treatment. The categories and ranges of scores for improvement are: 20-39 points being minimal improvement, 40-59 points being moderate improvement, and ≥ 60 points being major improvement
- Proportion of patients from start to end of KZR-616 treatment meeting International Myositis Assessment and Clinical Studies Group (IMACS) Definition of Improvement (DOI). The IMACS DOI is $\geq 20\%$ improvement in at least 3 of 6 core set activity measures, with no more than 2 core set activity measures (CSAMs) worsening by $\geq 25\%$ (the Manual Muscle Testing-8 Muscle Groups [MMT-8] cannot be a worsening measure)
- Absolute change and percent change from start to end of KZR-616 treatment in the IMACS individual CSAMs
- For patients with DM, the mean change from start to end of KZR-616 treatment in the Cutaneous Dermatomyositis Disease Area and Severity Index (CDASI)
- For patients with DM, the mean change from start to end of KZR-616 treatment in the Peak Pruritus Numeric Rating Scale (NRS).

Exploratory efficacy endpoints are:

- Mean change over time from start to end of KZR-616 treatment in the TIS in all patients, patients with DM only, and in patients with PM only
- Proportion of patients over time with an increase of ≥ 20 , ≥ 40 , or ≥ 60 points on the TIS from start to end of KZR-616 treatment in all patients, in patients with DM only, and in patients with PM only
- For patients with an increase of ≥ 20 points on the TIS from Baseline to W16, the proportion of patients with no change or increase in their TIS at W32 for all patients, in patients with DM only, and in patients with PM only
- Mean change and mean percent change over time from start to end of KZR-616 treatment in the IMACS individual CSAMs and core set damage measures (CSDMs) for all patients, in patients with DM only, and in patients with PM only
- Mean change from Baseline over time from start to end of KZR-616 treatment in the FI-2, the FI-3 and the individual components of the FI-3 for all patients, in patients with DM only, and in patients with PM only
- For patients with DM, mean change over time from start to end of KZR-616 treatment in the CDASI

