3.2. Minimization of Bias

3.2.1. Randomization

Patients will be allocated to a randomized treatment sequence (Arm A: KZR-616 followed by placebo; Arm B: placebo followed by KZR-616) in a 1:1 fashion. Patients will receive the first assigned study drug treatment in Treatment Period 1 (W0 through before dosing at W16)

and cross over to receive the next study drug treatment beginning on the first day of Treatment Period 2 (administration of the first dose at W16 through W32). Patients will be stratified according to their diagnosis of PM or DM. Patients will be stratified by their diagnosis of DM or PM.

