7.2.4.1. Total Improvement Score

The Myositis Response Criteria are recommended for use as primary endpoints in myositis therapeutic trials. The criteria use the 6 IMACS core set measures, combining the absolute percentage change in each with varying weights to obtain a TIS on a scale of 0-100. Different thresholds of improvement have been set for minimal, moderate, and major response. The TIS may be used as a continuous outcome measure or as a categorical outcome of improvement (minimal, moderate, or major improvement). The TIS can be calculated using the 2016 ACR/EULAR criteria² using the web calculator located at:
https://www.niehs.nih.gov/research/resources/imacs/response_criteria/adult.html

The User's Guide is located at:

https://www.niehs.nih.gov/research/resources/imacs/response_criteria/users_guide_for_the_adult.html

[dult_dermatomyositis_and_polymyositis_response_criteria_online_calculator_508.pdf](https://www.niehs.nih.gov/research/resources/assets/docs/duilt_dermatomyositis_and_polymyositis_response_criteria_online_calculator_508.pdf)
(Last accessed: 28 February 2019)

Investigators will not be required to make these calculations for the study.

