10. STATISTICAL ANALYSES

A detailed Statistical Analysis Plan (SAP) will be prepared for approval by the Sponsor prior to performing any unblinded analysis for presentation to personnel designated as being blinded to the randomization.

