10.1. Sample Size Calculation

Prior summary statistics on change from Baseline in TIS score are not available. Hence, statistical power is quantified via standardized effect size (mean difference divided by pooled standard deviation [SD]). A sample size of 24 patients has 80% power to yield a statistically significant ($\alpha=0.05$ 2-sided) improvement from Baseline if the true underlying effect size is 0.6 (90% power if true effect size is 0.7). The minimum observed effect size that would yield statistical significance is 0.42. This level of statistical precision is thought to be adequate for this initial trial of KZR-616 in PM and DM.

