10.3. Efficacy Analysis

The primary endpoint is mean change from start to end of KZR-616 treatment in TIS.² For the continuous efficacy parameters, within-patient changes will be analyzed as follows:

- (1: primary) by comparing the Baseline and post Baseline observations within patients for the KZR-616 treatment periods combined, ie, W16 versus W0 for patients allocated to the randomized treatment sequence KZR-616 followed by placebo and W32 versus W16 for patients allocated to the randomized treatment sequence placebo followed by KZR-616, combined;
- (2: secondary) by comparing the change from Baseline in Treatment Period 1 between treatments, ie, change from W0 to W16 for patients allocated to the randomized treatment sequence KZR-616 followed by placebo versus change from W0 to W16 for patients allocated to the randomized treatment sequence placebo followed by KZR-616; and
- (3: exploratory) by comparing the last response on test treatment between treatments via a crossover design analysis, ie, W16 for patients allocated to the randomized treatment sequence KZR-616 followed by placebo and W32 for patients allocated to the

randomized treatment sequence placebo followed by KZR-616, combined, versus W16 for patients allocated to the randomized treatment sequence placebo followed by KZR-616 and W32 for patients allocated to the randomized treatment sequence KZR-616 followed by placebo, combined.

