The rationale for this priority order is as follows. The usual crossover analysis for this design is prespecified as exploratory since it is unknown whether that analysis would be confounded by carryover effect. In order to maximize the precision for assessment of KZR-616 effect, it is assessed primarily via all patients' Baseline versus post-Baseline KZR-616 assessment and secondarily by the Treatment Period 1 between-treatment comparison. Summary statistics, including 95% confidence intervals, will be provided for each treatment for each of the 3 types of analysis. Within-patient changes will be analyzed via paired t-tests and corroborated by signed rank tests. Between-patient differences will be analyzed via analysis of covariance, with Baseline as a covariate. The crossover analysis will be via a mixed-model repeated-measures analysis. Normality will be assessed graphically and via the Shapiro-Wilk statistic. If substantial departure from normality is observed, transformations, eg, natural log and rank, will be explored. P values will be 2-sided with at the type 1 error level 0.05.

Binary endpoints will be summarized by counts and percent and 95% confidence intervals via Clopper-Pearson method. Additional analyses will be specified in the SAP.

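### Period 1 between-arm comparison of TIS: the only named covariate is 0 for every patient and the PM/DM stratification factor is not in the model, so the test is valid but conservative if diagnosis predicts TIS

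*Combined protocol and SAP*

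**What the plan says.** Section 10.3 ranks three analyses of the continuous endpoints. The second is made "by comparing the change from Baseline in Treatment Period 1 between treatments", that is, Week 0 to Week 16 in Arm A against Arm B. Its model is given in one sentence, repeated in the synopsis: "Between-patient differences will be analyzed via analysis of covariance, with Baseline as a covariate". No other covariate is named.

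Section 7.2.4.1 describes TIS as a composite of the six IMACS core set measures, "combining the absolute percentage change in each with varying weights to obtain a TIS on a scale of 0-100". Section 3.1 defines Baseline as Day 1 of Week 0.

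Section 3.2.1 says: "Patients will be stratified according to their diagnosis of PM or DM". Section 2.2.1 lists, among the exploratory endpoints, mean change over time "in the TIS in all patients, patients with DM only, and in patients with PM only". Neither the Period 1 model nor any other model in Section 10 is given a diagnosis term.

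Section 10 leaves detail to a later document: "A detailed Statistical Analysis Plan (SAP) will be prepared for approval by the Sponsor". Section 10.3 adds that further analyses will be specified there. The supplied text contains no separate SAP.

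**The concern.** Two gaps meet in one model. First, a score built from change since Baseline equals 0 at Baseline. The protocol does not say this in words, but it follows from the definition. For TIS the named covariate is therefore a constant and explains nothing.

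Second, stratified randomisation balances PM and DM across the arms. The treatment estimate then carries little or none of the PM-DM difference, but the residual variance of an unadjusted test still does. If the two diagnoses respond differently on TIS, the standard error is too large for the design actually run.

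This comparison is the highest-ranked one against concurrent placebo: the primary analysis is within-patient and the crossover analysis is exploratory. With about 12 patients per arm, precision is scarce, and Section 10.3 itself gives precision as a reason for its order of analyses.

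**Working it through.** **1. The plan's own figure.** Section 10.1 concerns the primary paired test: N = 24, two-sided alpha 0.05. A paired t-test with 23 df gives 80.4% power at an effect size of 0.6 and 90.7% at 0.7. The smallest significant observed effect is t(0.975, 23)/√24 = 0.422. The stated 80%, 90% and 0.42 are reproduced. No power is stated for the between-arm comparison.

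**2. The Baseline term.** For TIS the design has three columns: intercept, arm and Baseline. With Baseline = 0 throughout, its rank is 2. The model is a two-sample t-test with 24 − 2 = 22 df.

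**3. The stratum.** Inputs from the plan are 12 per arm (synopsis) and alpha 0.05 two-sided (Section 10.3). Assumptions are a normal outcome with total SD 1, exact balance of arms within strata, no missing data, and a share R² of TIS variance explained by diagnosis. The documents give no value for R², so a range is shown.

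- True SD of the difference in means: √(2(1 − R²)/12).
- Pooled sum of squares in the planned test: (1 − R²) times a noncentral chi-square with 22 df and noncentrality 24R²/(1 − R²).
- Standard error excess: √(1 + (24/22) × R²/(1 − R²)) − 1. At R² = 0.10: √(1 + 1.0909 × 0.1111) − 1 = 0.059.
- Planned test: rejection probability integrated over that distribution, with the critical t at 22 df.
- With the stratum: noncentral t, 21 df, noncentrality δ/√(2(1 − R²)/12).
- Implied PM-DM gap with equal strata: 2√(R²/(1 − R²)) within-stratum SD.

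| R² | 0% | 5% | 10% | 20% | 30% |
|---|---|---|---|---|---|
| PM-DM gap (within-stratum SD) | 0 | 0.46 | 0.67 | 1.00 | 1.31 |
| Standard error excess, planned | 0% | 3% | 6% | 13% | 21% |
| Type 1 error, planned | 5.0% | 4.4% | 3.9% | 2.8% | 1.9% |
| Power at 1.2 SD, planned | 80.2% | 80.6% | 81.1% | 82.1% | 83.3% |
| Power at 1.2 SD, with stratum | 80.0% | 82.0% | 84.0% | 88.0% | 91.8% |
| Power at 0.6 SD, planned | 29.0% | 28.4% | 27.8% | 26.3% | 24.6% |
| Power at 0.6 SD, with stratum | 28.9% | 30.2% | 31.5% | 34.8% | 38.9% |
| Effect with 80% power, planned (SD) | 1.197 | 1.191 | 1.184 | 1.170 | 1.155 |
| Effect with 80% power, with stratum (SD) | 1.200 | 1.169 | 1.138 | 1.073 | 1.004 |

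Effects are in units of total SD, so the within-stratum SD shrinks as R² grows. This is why planned power at 1.2 SD rises slightly along the row. The 0.6 SD is illustrative: Section 10.1 uses it for within-patient "improvement from Baseline if the true underlying effect size is 0.6", not for a difference between arms.

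**4. Cross-check by simulation.** With permuted blocks of 4 within strata and 12 DM and 12 PM patients, the planned test had type 1 error 4.4, 2.8, 1.4 and 0.6% at gaps of 0.5, 1.0, 1.5 and 2.0 within-stratum SD. With the stratum it was about 5% throughout. With 9, 13, 18 or 20 DM patients and blocks of 2, 4 or 6, the planned test stayed below 5% at every gap tried (0.5 to 1.5). When the 12:12 allocation was not stratified, the unadjusted test had about 5%, so the conservatism comes from the stratification.

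**5. Less ideal conditions.** The best-case cost of the extra term at R² = 0 is 0.1 points of power at 0.6 SD and 0.2 at 1.2 SD. Break-even is then at R² of about 0.3% (0.6 SD) to 0.6% (1.2 SD). With random stratum sizes, blocks of 4 and an assumed 15% missing, at 1.2 SD:

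- R² = 0: a cost of about 0.9 points (72.1 to 71.2%).
- R² = 5%: a gain of about 1 point; type 1 error of the planned test is 4.7 to 4.8%.
- R² = 10%: a gain of about 3 points.

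Break-even is then roughly 2 to 3% of variance.

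**The case against.** **The SAP may already cover it.** Section 10 promises a detailed SAP, Section 10.3 is written at summary level, and its sentence on covariates does not exclude others. This stands in part. A reader might infer that the final analysis will omit diagnosis; the documents do not show that. They show only that the model as written does not name it.

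**Nothing shows that diagnosis matters.** This stands. Section 10.1 says: "Prior summary statistics on change from Baseline in TIS score are not available". The larger gains need PM-DM gaps of 1.0 within-stratum SD or more, and at R² = 5% the gain is small.

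**The Baseline half has no numerical effect of its own.** This also stands. A constant simply drops out, and every figure in the table comes from the stratum. A reader might infer that adjusting for Baseline is a mistake in general. It is not: for the core set measures and other endpoints whose Baseline varies, it is sound.

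**The extra term is not quite free.** The cost of 0.1 to 0.2 points and the break-even of 0.3 to 0.6% hold only with exact balance and complete data. Section 4.1 plans approximately 24 patients, Section 8.2 does not replace withdrawals, and no block size or PM/DM split is given. The realistic cost is nearer 1 point and break-even nearer 2 to 3%. The direction does not change.

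**Normal-theory figures for a score bounded at 0 and 100 are approximate.** This is fair, and Section 10.3 allows transformation. The figures show size, not precision.

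**Conclusion.** For TIS, the Period 1 ANCOVA as written is an unadjusted two-sample t-test, and the stratification factor is not in it. If diagnosis predicts TIS, the test is unbiased and valid but conservative: type 1 error falls from 5.0% to between 4.4 and 1.9% for R² of 5 to 30%, given exact 12 v 12 balance. If diagnosis does not predict TIS, nothing is lost.

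Three stronger readings are not supported. The comparison is not biased and does not inflate false positives, because stratification balances diagnosis between arms. The primary paired test and its sample size are not touched. The stratum also does not rescue a small effect: at 0.6 SD, power stays below 40% in every scenario shown.

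This is a worthwhile efficiency improvement to a secondary analysis, not an error that affects the primary conclusion.

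**What to change.** In Section 10.3, the matching synopsis text and the SAP:

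- Add PM/DM stratum to the Period 1 between-arm model for TIS.
- State that the Baseline term does not apply to TIS because it is 0 for all patients.
- Optionally, add the same stratum term for other continuous endpoints measured in both diagnoses, keeping each endpoint's own Baseline. No gain was calculated for these.
- Do not add it for CDASI or Peak Pruritus NRS. Sections 7.2.4.9 and 7.2.5.8 restrict them to DM patients, so diagnosis cannot be estimated there.
- Leave the primary paired test and the crossover model as they are.

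The change is wording only and needs no new data. It uses one of 22 df. If diagnosis is not prognostic, the price is 0.1 to 0.2 points of power in the best case and about 1 point at 1.2 SD in the less ideal case. Fixing the model before unblinding also removes any later choice between adjusted and unadjusted results.

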10.4. Safety Analysis

The safety analysis set will be used for all presentations of safety endpoints. No statistical testing will be used to compare treatment groups for different safety endpoints. Safety data will be summarized descriptively for each test treatment. All AEs will be coded using the current version of the MedDRA. Treatment emergent AEs will be presented within summary presentations, by MedDRA system organ class, preferred term, and treatment group.

Additional analyses will be specified in the SAP.

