- (3: exploratory) by comparing the last response on test treatment between treatments via a crossover design analysis, ie, W16 for patients allocated to the randomized treatment sequence KZR-616 followed by placebo and W32 for patients allocated to the randomized treatment sequence placebo followed by KZR-616, combined, versus W16 for patients allocated to the randomized treatment sequence placebo followed by KZR-616 and W32 for patients allocated to the randomized treatment sequence KZR-616 followed by placebo, combined.

The rationale for this priority order is as follows. The usual crossover analysis for this design is prespecified as exploratory since it is unknown whether that analysis would be confounded by carryover effect. In order to maximize the precision for assessment of KZR-616 effect, it is assessed primarily via all patients' Baseline versus post-Baseline KZR-616 assessment and secondarily by the Treatment Period 1 between-treatment comparison. Summary statistics, including 95% confidence intervals, will be provided for each treatment for each of the 3 types of analysis. Within-patient changes will be analyzed via paired t-tests and corroborated by signed rank tests. Between-patient differences will be analyzed via analysis of covariance, with Baseline as a covariate. The crossover analysis will be via a mixed model repeated measures analysis. Normality will be assessed graphically and via the Shapiro-Wilk statistic. If substantial departure from normality is observed, transformations, eg, natural log and rank, will be explored. P values will be 2-sided with the type 1 error level at 0.05.

Binary endpoints will be summarized by counts and percent and 95% confidence intervals via Clopper-Pearson method. Additional analyses will be specified in the Statistical Analysis Plan (SAP).

Safety Analysis

The safety analysis set will be used for all presentations of safety endpoints. No statistical testing will be used to compare treatment arms for different safety endpoints. Safety data will be summarized descriptively for each test treatment. All AEs will be coded using the current version of the Medical Dictionary for Regulatory Activities (MedDRA). Treatment emergent AEs will be presented within summary presentations by MedDRA system organ class and preferred term, cohort, and treatment arm.

Pharmacokinetic and Pharmacodynamic Analyses

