3.1.3. Study Design Rationale

This placebo-controlled double-blind crossover study is designed to minimize bias in the evaluation of KZR-616 in patients with DM/PM and to maximize the opportunity for each patient to contribute data. All patients may still receive background treatment in the form of the allowed concomitant therapies as described in the study exclusion criteria ([Section 4.3](#)). A crossover design was selected for use in this study to:

- Increase the power of the study because not only will there be the opportunity for evaluation of between-group comparisons, but the patients initially treated with placebo can serve as their own controls
- Data for bortezomib allude to maintenance of effect of proteasome inhibition postdosing.³ The Treatment and SFU Periods allow for evaluation of the treated population after drug discontinuation in terms of both safety and efficacy; these data are best obtained from those patients that start on KZR-616 first and then cross over to placebo.

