9.1.5. Follow-up on Adverse Events

Adverse events are intended to be collected according to the procedures outlined above from the time of informed consent and to continue for 30 days following the last dose, or the End of Study Visit, whichever occurs later.

All Investigators should follow up with patients with AEs until the event is resolved or until, in the opinion of the Investigator, the event is stabilized or determined to be chronic. Details of AE resolution must be documented in the eCRF.

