10.2. Analysis Populations

The Safety Analysis Set consists of all patients who receive at least 1 dose of the study drug.

The Full Analysis Set (FAS) consists of all patients who receive at least 1 dose of the study drug and who have a Baseline and post-Baseline observation. This is the primary efficacy analysis set for the study.

The Per Protocol Analysis Set consists of all patients in the FAS, excluding those identified as having relevant protocol deviations.

The PK Analysis Set consists of all patients who received at least 1 dose of KZR-616 and for whom the PK data are considered sufficient. Since this is a Phase 2 trial, all analyses and summaries will be based on the actual test treatment the respective patients received.

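### Safety summaries by treatment received pool Arm A's placebo time straight after KZR-616 with drug-naive placebo time, which could understate the KZR-616 contrast if late-onset effects exist

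*Combined protocol and SAP*

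**What the plan says.** Section 10.4 sets the basis for safety reporting: "Safety data will be summarized descriptively for each test treatment", with no statistical testing between groups. Section 10.2 adds the general principle that "all analyses and summaries will be based on the actual test treatment the respective patients received".

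The columns of the adverse event tables are named in two ways. Section 10.4 tabulates treatment-emergent events "by MedDRA system organ class, preferred term, and treatment group"; the synopsis tabulates them "by MedDRA system organ class and preferred term, cohort, and treatment arm". Section 10.4 closes with "Additional analyses will be specified in the SAP", and the opening of Section 10 says that this SAP is still to be prepared.

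For efficacy, Section 10.3 is more guarded: "The usual crossover analysis for this design is prespecified as exploratory since it is unknown whether that analysis would be confounded by carryover effect". It ranks a between-arm comparison confined to Treatment Period 1 ahead of the crossover analysis.

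Section 3.1.3 gives persistence as one reason for the design: "Data for bortezomib allude to maintenance of effect of proteasome inhibition postdosing". It regards patients who take KZR-616 first as the best source of safety and efficacy data after the drug is stopped. Under Section 9.1.5, adverse event collection is to "continue for 30 days following the last dose, or the End of Study Visit, whichever occurs later".

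**The concern.** Table 1 and the visit schedules move Arm A from KZR-616 to placebo one dosing interval apart. On the natural reading of Sections 10.2 and 10.4, an adverse event that starts in Arm A during Period 2 falls under placebo, whatever caused it. The protocol text gives no definition of treatment-emergent, no rule that assigns an event to a period, no lag window and no Period 2 safety baseline (Baseline is Day 1 of W0).

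Some persistence is plausible from the protocol itself. Section 1.3 describes irreversible inhibition and incomplete recovery of PBMC activity within 6 days of a dose. Section 1.4 reports that plasma cell formation is blocked in vitro. The plan takes carryover seriously enough to make the efficacy crossover analysis exploratory, yet gives safety neither a Period 1 comparison nor a separate display of post-KZR-616 time.

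Safety and tolerability is a secondary objective, reported only descriptively. With about 12 patients per arm, one or two events in the wrong column would change how a table reads. A misplaced event leaves the KZR-616 column and enters the placebo column, so any error from this source narrows the contrast.

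**Working it through.** The plan gives no figure for the safety analysis. Its sample-size figures (Section 10.1) concern the primary efficacy test. They reproduce with a paired t-test on 24 patients (80.4% power at effect size 0.6, stated as 80%), and nothing here alters them.

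**Inputs from the documents**
- Last KZR-616 dose in Arm A: W15, Day 106 (Tables 1 and 3).
- First placebo dose in Arm A: W16, Day 113 (Tables 1 and 4).
- End of Period 2: W32, Day 225. End of follow-up: W40, Day 281 (Table 4).
- About 12 patients per arm, 1:1 (synopsis, Section 3.2.1).

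**Share of placebo time that follows KZR-616**
1. Each arm supplies one placebo period per patient: 12 + 12 = 24 patient-periods, of which 12 (50%) follow KZR-616.
2. Arm A's Period 2 lasts 225 − 113 = 112 days.
3. Thirty days after the last KZR-616 dose is Day 106 + 30 = 136, and 136 − 113 = 23 days. Then 23/112 = 20.5% of Arm A's Period 2, and 23/(112 + 112) = 10.3% of all placebo treatment-period time.
4. With nine weeks instead (the post-dose follow-up interval for early withdrawals in Section 8.2), the window ends on Day 169. That gives 56 days: 56/112 = 50% of Arm A's Period 2 and 56/224 = 25% of placebo treatment-period time.
5. If Arm A's W32 to W40 follow-up also counted as placebo time, Arm A would supply 281 − 113 = 168 days. The 30-day shares would fall to 23/168 = 14% and 23/(168 + 112) = 8%.

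**Effect on the contrast**

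Let r be the drug-caused risk per KZR-616 course and f the share of those events that start after the course's treatment period ends. Both are assumptions; the documents give neither. A background risk equal in both columns cancels from the difference and is set to 0 here.
- KZR-616 column: the mean of r(1 − f) in Arm A and r in Arm B is r(1 − f/2), if Arm B's late events in follow-up count under KZR-616.
- Placebo column: the mean of rf in Arm A and 0 in Arm B is rf/2.
- Difference: r(1 − f).
- If Arm B's late events are not counted, the KZR-616 column is r(1 − f) and the difference is r(1 − 1.5f).
- Expected misplaced events in Arm A: 12rf.

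For r = 10%:

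| f | KZR-616 | Placebo | Difference (points) | Difference if Arm B late events not counted | Misplaced events in Arm A |
|---|---|---|---|---|---|
| 0 | 10.0% | 0.0% | 10.0 | 10.0 | 0 |
| 10% | 9.5% | 0.5% | 9.0 | 8.5 | 0.12 |
| 25% | 8.75% | 1.25% | 7.5 | 6.25 | 0.30 |
| 50% | 7.5% | 2.5% | 5.0 | 2.5 | 0.60 |

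With r = 25% and f = 50%, misplaced events reach 12 × 0.25 × 0.5 = 1.5. With f = 0 there is no distortion at any r.

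**The case against.** The strongest reply is that the plan has a gap here, not a stated rule. Treatment group is undefined in Section 10.4. The synopsis tabulates by treatment arm, and the arms are sequences, so that table would not pool the two kinds of placebo time. A missing attribution rule could still be supplied in the SAP. This stands in part: the pooling is the natural reading of Sections 10.2 and 10.4, not an explicit instruction. The two labels still need reconciling.

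The second reply is pharmacological. The half-life is under 2 hours (Section 6.2.1.2). Weekly dosing is described as serial episodic dosing without accumulation (Section 1.3). The systemic reactions seen so far began about 8 to 24 hours after dosing (Sections 1.3 and 6.1.3) and would be assigned correctly. Bortezomib is a different, nonselective drug. All of this stands, and it means that the effect may be small or nil.

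A reader might infer more than the documents support:
- **That the plan will understate KZR-616's risk.** This requires late-onset or persisting effects, which are possible but not shown.
- **That Arm B has a 63-day tail under KZR-616 against 7 days in Arm A.** No section says where W32 to W40 events are counted.
- **That the 30-day period in Section 9.1.5 is an attribution window.** It governs how long events are collected. Section 9.2.2 counts its SAE period from the last dose of KZR-616 or placebo, which for a completing Arm A patient is a placebo dose.
- **That the zoster SAE in Section 1.3 shows delay.** It arose during the dosing course, after three doses.
- **That Arm A's W16 laboratory values are misassigned.** Samples at dosing visits are taken before the dose (Section 7.2.6.10), so they reflect KZR-616. Only changes that persist or emerge later are exposed.

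**Conclusion.** The point holds as a conditional one. As written, Sections 10.2 and 10.4 lead to a placebo column of which half the patient-periods directly follow KZR-616, with no safeguard like the one that Section 10.3 gives efficacy. If late-onset or persisting effects exist, the KZR-616 versus placebo contrast could be understated: by the fraction f under the simple model, or 1.5f if Arm B's follow-up events are left out. The documents do not allow f to be estimated, and the understatement is zero if f is zero. The exposure figures (21% of Arm A's Period 2 and 10% of placebo treatment-period time within 30 days) show where misplacement could occur, not how much does. They assume equal arms, full attendance and the nominal visit days. The different column labels in the synopsis and Section 10.4 are a defect in their own right. The change is worth making because it is cheap and gives a cleaner contrast.

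**What to change.** In Section 10.4, carried through to the synopsis and SAP:

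(a) Make Treatment Period 1 (Arm A on KZR-616 versus Arm B on placebo, W0 to W16) the main controlled safety table.

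(b) Show Arm A's Period 2 as its own column, labelled as placebo after KZR-616, and do not pool it with drug-naive placebo.

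(c) State how events from W32 to W40 are assigned in each arm, and use one column definition in the synopsis and Section 10.4.

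(d) As a sensitivity table only, assign to KZR-616 the adverse events, other than injection-site events, that start within 30 days of its last dose. This should not be the main rule, because four placebo injections (Days 113, 120, 127 and 134) fall inside that window and reactions to them would be labelled as KZR-616.

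The cost is some wording, one extra column and one extra table. Section 9.1.6 already requires the date of first occurrence for each event, so no new data or patients are needed. The downside is that the clean placebo column rests on about 12 patients, and the sensitivity table will credit some unrelated events to KZR-616.
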